5.10 Analysis of Efficacy Data

Efficacy analyses will be performed on the mITT and PP populations. For change from baseline of ADAS-Cog total score, MMSE total score, ADCS-ADL total score, CDR-SB total score, NPI total score, A repeated-measures mixed-effects model with treatment (Arm 1 + Arm 2 vs. Arm 3, Arm 1 vs. Arm 3 and , Arm 2 vs. Arm 3), study visit, time-by-treatment, APOE4 status, and baseline as a covariate will be used to analyze change from baseline. The least square means using maximum likelihood estimate and its 95% will be provided. The unstructured covariance will be used in the modeling of the within-patient errors in the analysis.

For change from baseline of mean SUVR, A repeated- measures mixed-effects model with treatment (Arm 1 + Arm 2 vs. Arm 3, Arm 1 vs. Arm 3 and, Arm 2 vs. Arm 3), study visit, time-by-treatment, APOE4 status, and baseline as a covariate will be used to analyze change from baseline. The unstructured covariance will be used in the modeling of the within-patient errors in the analysis.

For change from baseline of mean SUVR by region, A repeated- measures mixed-effects model with treatment (Arm 1 + Arm 2 vs. Arm 3, Arm 1 vs. Arm 3 and, Arm 2 vs. Arm 3), study visit, time-by-treatment, and baseline as a covariate will be used to analyze change from baseline. The unstructured covariance will be used in the modeling of the within-patient errors in the analysis.

The p-values and confidence intervals for these efficacy endpoints were not adjusted for multiplicity, it should be used for screening purposes only, and that one side of 95% confidence intervals are provided to help gauge the precision of the estimates for treatment difference.

The proportion of PET positive subjects with visual read will be provided by number and percentage for each treatment group in mITT Population and PP Population at each post treatment scheduled visit. Treatment differences will be analysed with the Chisq test. The one-sided 95% confidence interval (CI, right side) between (Arm 1 + Arm 2 vs. Arm 3, Arm 1 vs. Arm 3 and, Arm 2 vs. Arm 3) from all visits will be calculated.

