3 STUDY DESIGN

This is a 78-week, multicenter, randomized, double-blind, placebo-controlled Phase IIa study. Eligible subjects, 60 years or older with mild Alzheimer’s disease (AD), will be further screened by ¹⁸F-AV-45 PET scan for the presence of amyloid deposition.

Enrolled subjects will be randomized into one of the 3 treatment arms in 1:1:1 ratio. Subjects assigned to Arm 1 will receive 7 doses of UB-311 at Weeks 0, 4, 12, 24, 36, 48, and 60.

Subjects assigned to Arm 2 will receive 5 doses of UB-311 at Weeks 0, 4, 12, 36, and 60, and placebo at Weeks 24 and 48. Subjects assigned to Arm 3 will receive placebo at Weeks 0, 4, 12, 24, 36, 48, and 60. Subjects will be followed until Week 78. Subjects enrolled in the Phase I trial with UB-311 will be excluded from the Phase IIa trial.

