 - The MMSE is a 30-point questionnaire that is used extensively in clinical and research settings to measure cognitive impairment and is commonly used in medicine and allied health to screen for dementia. It is also used to estimate the severity and progression of cognitive impairment and to follow the course of cognitive changes in an individual over time; thus making it an effective way to document a participant’s response to treatment. The total score range is 0 – 30 and lower scores indicating greater impairment.
- Function: ADCS-ADL score is range of 0-78 and lower scores indicating greater impairment
- Global: CDR-SB

- The CDR-SB includes six domains (0-3 points/domain), with a total scoring range of 0 – 18 and higher scores indicating greater impairment. The CDR score is calculated at baseline for eligibility check.
- Behavior: NPI:
 - The NPI has 12 domains and for each domain, the relatives assess the frequency of the behaviour (4-point scale), the severity of the symptom (3-point scale) and the emotional stress for the caregiver (6-point scale). The total score of NPI is 0-144 and lower scores indicates greater impairment.

ADAS-Cog, ADCS-ADL, and NPI are rated at baseline (V1), Week 28 (V6), Week 52 (V10) and Week 78 (V13), while MMSE and CDR/CDR-SB are assessed at the first screening (S1), Week 24 (V5), Week 48 (V9) and Week 78 (V13). If a patient withdraws from the study prematurely during the study period or does not have any or some of the scores, the data will be treated as missing values, and no procedure for handling missing assessments will be applied.

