5 STATISTICAL METHODS

5.1 General

Continuous data will be summarized by treatment group using the number of observations available (n), mean, standard deviation (SD), median, interquartile range (IQR), minimum, and maximum.

Categorical data will be summarized by treatment group using count and percentage. Missing data will not be categorized in the summaries.

In general, descriptive statistics of quantitative efficacy and safety parameters (results and changes from baseline) by scheduled visit will be provided on observed cases, i.e. the inclusion of only subjects with non-missing assessments at a specific visit.

For undetected value, this study will take the minimum value that can be detected as the text value, eg, <3.5 will be treated as 3.5 and <0.012 will be treated as 0.012 when performing the summary and will list the original value in listing.

- The pre-treatment period is defined as the time from the date of the informed consent to the time before the administration of first dose of study medication.
- The post-treatment period is defined as the time from after the first dose of study medication to the end of the study.

All statistical tests will be two-sided at the alpha level of 0.05, unless otherwise specified.

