5.11 Subgroup Analysis of Immunogenicity/Efficacy Data

Subgroup analysis by APOE4 carrier will be performed for all immunogenicity and efficacy data, and the analysis model will be the same as the overall analysis.

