Overall change from baseline for ARWMC frequency by visit will be summarized for safety population by treatment with number and percent of patients.

Visit value and Change from baseline for ARWMC will be summarized for safety population by treatment with n, mean, std dev, CV, Q1, median, Q3, Min, Max, L95 and U95.

Overall change from baseline for post- vaccine meningoencephalitis frequency by visit will be summarized for safety population by treatment with number and percent of patients.

5.13 **Sample Size**

This early phase clinical trial is exploratory in nature; hence, the sample size is determined to assess the primary objective of safety, tolerability, and immunogenicity of UB-311. The total of 45 subjects is planned to be enrolled, 15 per arms. For each UB-311-treated arm, 15 subjects are thought to be sufficient to detect an adverse event with an incidence of 7%. Furthermore, 30 subjects receiving UB-311 are anticipated to be able to detect an adverse event with an incidence of 4%.

With the current sample sizes, there may be limited power to detect a reduction in mean SUVRs or regional SUVRs unless there is a dramatic clearance of pre-existing plaques, and extremely limited power to detect effects on cognitive and functional endpoints. These analyses are therefore considered exploratory.

5.14 **Interim Analysis**

There is no interim analysis for this study.

5.15 **Multiplicity**

There is only primary immunogenicity endpoint in this study, and all efficacy endpoint will be served as secondary endpoint, and p-Value and its confidence interval will be used for screening purpose, so there is no multiplicity adjustment performed.

5.16 **General Conventions for Tables, Listings and Figures**

For summary tables, unless otherwise specified, the number of decimal places provided in the SAS output will be based on the accuracy of the least accurate value in the raw data as follows:

- n integer
- Arithmetic mean 1 decimal place more than the least accurate number in the raw data
- SD 2 decimal place more than the least accurate number in the raw data
- CV(%) 2 decimal places
- Geometric mean 1 decimal place more than the least accurate number in the raw data
- Median 1 decimal place more than the least accurate number in the raw data
- Minimum same number of decimal places as raw data

- Maximum same number of decimal places as raw data
- Confidence interval same number of decimals as the associated statistic

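### SAP 5.10 names maximum likelihood, with no small-sample correction, for the five clinical-scale mixed models at N=45; followed literally, standard errors are about 5-6% too small

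*SAP*

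**What the plan says.** SAP 5.10 analyses change from baseline in ADAS-Cog, MMSE, ADCS-ADL, CDR-SB and NPI with a repeated-measures mixed model. Its terms are treatment plus "study visit, time-by-treatment, APOE4 status, and baseline as a covariate will be used to analyze change from baseline". On estimation it says: "The least square means using maximum likelihood estimate and its 95% will be provided". The noun after the percentage is missing. On covariance: "The unstructured covariance will be used in the modeling of the within-patient errors in the analysis".

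Other statements that bear on the point:

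- Size (SAP 5.13): "The total of 45 subjects is planned to be enrolled, 15 per arms".
- Error level (SAP 5.1): "All statistical tests will be two-sided at the alpha level of 0.05, unless otherwise specified".
- Intervals: SAP 5.10 gives one-sided 95% intervals for treatment differences, so that readers can judge how precise the estimates are.
- Populations: SAP 5.10 runs the models on both the mITT and the per-protocol sets.
- Subgroups: SAP 5.11 repeats all immunogenicity and efficacy analyses by APOE4 carrier status, and "the analysis model will be the same as the overall analysis". SAP 5.9 drops the APOE4 term from the mixed model within those strata.
- Status: SAP 5.10 and 5.15 describe the efficacy p-values and intervals as unadjusted and for screening. SAP 5.13 calls the SUVR, cognitive and functional analyses exploratory.

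Maximum likelihood is named only in the clinical-scale paragraph. The composite SUVR and regional SUVR paragraphs of 5.10 and the antibody model in 5.9 name no estimator. REML, Kenward-Roger and Satterthwaite appear in neither document.

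**The concern.** Maximum likelihood estimates the covariance as though the mean parameters were known. It makes no allowance for the degrees of freedom spent on arms, visits, APOE4 and baseline, so variances are biased downward. With hundreds of subjects the effect is negligible. With 15 per arm it is visible, and it is larger in the per-protocol and APOE4 fits.

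Two things are at stake for the five scales. Tests nominally at 5% reject too often under the null. Intervals offered as a guide to precision are systematically too narrow.

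**Working it through.** **The plan's own figure.** There is none to reproduce. The documents state no standard error, power or error rate for these models. The sample-size statement concerns detecting an adverse event and does not bear on this point. The benchmark is the 5% level in SAP 5.1.

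**Inputs from the documents.** N = 45 in three equal arms (SAP 3 and 5.13). Three post-baseline assessments per scale (SAP 4.3): Weeks 28, 52 and 78 for ADAS-Cog, ADCS-ADL and NPI; Weeks 24, 48 and 78 for MMSE and CDR-SB. Mean parameters per visit: 3 arms + APOE4 + baseline = 5. Within an APOE4 stratum the APOE4 term drops out, leaving 4.

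**Closed form, complete data.** The ML variance is (N − p)/N of the unbiased variance, so

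- SE ratio, ML to unbiased: r = √((N − p)/N)
- two-sided type I error, t reference: P(|t with N − p df| > r × t₀.₉₇₅)
- one-sided 95% coverage: 1 − P(t with N − p df > r × t₀.₉₅)

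At N = 45 and p = 5:

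- r = √(40/45) = 0.943, so the SE is 5.7% too small.
- t reference: 2.021 × 0.943 = 1.906, which gives 6.4%.
- Normal reference: 1.960 × 0.943 = 1.848, which gives 7.2%.
- One-sided: 1.684 × 0.943 = 1.588, a tail of 6.0%, so coverage is 94.0%.

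**Smaller planned fits.** The documents give no carrier rate, dropout rate or per-protocol size. The sizes below are assumptions, shown as a range.

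| Set | N | p | r | Type I, t | Type I, normal | One-sided coverage |
|---|---|---|---|---|---|---|
| All subjects | 45 | 5 | 0.943 | 6.4% | 7.2% | 94.0% |
| Per-protocol | 36 | 5 | 0.928 | 6.8% | 7.9% | 93.7% |
| Per-protocol | 30 | 5 | 0.913 | 7.2% | 8.6% | 93.4% |
| APOE4 stratum | 25 | 4 | 0.917 | 7.0% | 8.7% | 93.5% |
| APOE4 stratum | 20 | 4 | 0.894 | 7.6% | 9.9% | 93.1% |

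**Simulation of the SAP model at N = 45.** The closed form treats the APOE4 and baseline effects as separate at each visit. The SAP model as listed has them common across visits: 9 arm-by-visit means + 2 = 11 parameters. That model was simulated under the null with three visits and an unstructured covariance, and fitted by ML and by REML. Assumptions: AR(1) correlation 0.6, 50% APOE4 carriers, and no dropout (3,000 runs) or 20% monotone dropout (2,000 runs). The t reference used completers minus 5 degrees of freedom. The paired figures are Arm 1 versus placebo and pooled active arms versus placebo, at the last visit.

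| Dropout | SE ratio ML/REML | ML, t | ML, normal | REML, t |
|---|---|---|---|---|
| 0% | 0.951 | 6.5%, 6.7% | 7.5%, 7.5% | 5.3%, 5.7% |
| 20% | 0.944 | 6.0%, 6.3% | 7.2%, 7.3% | 4.5%, 4.8% |

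Simulation error is about 0.4 to 0.5 percentage points on each rate. The simulation agrees with the closed form: SEs are 4.9% to 5.6% too small under ML, and REML brings the error rate back to about 5%.

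**The case against.** **The wording may be loose.** The sentence is unfinished, it attaches maximum likelihood to the least-squares means and not to the covariance, and the phrase could be shorthand that covers REML. That is possible, and the SAP does not settle it. But the sentence does name an estimator, and a programmer following it would be entitled to fit by ML. Under either reading the degrees-of-freedom method is missing.

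**The consequence is small.** This stands. The endpoints are secondary, SAP 5.13 admits extremely limited power for cognition and function, and no decision rule depends on p < 0.05. Multiplicity matters more. Five scales × three contrasts × two populations is 30 unadjusted tests at a single visit. Under a global null that means 30 × 0.05 = 1.5 expected false positives at the nominal rate, and 30 × 0.064 = 1.9 at the ML rate for N = 45.

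**The larger error rates need inputs that the SAP does not give.** This also stands. Figures above 7.6% in the table require a normal reference, which the SAP does not specify. All subgroup and per-protocol figures depend on assumed sizes.

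**A broader reading is tempting.** A reader might infer that every efficacy p-value and interval, PET and antibody results included, is anti-conservative. The documents do not support that. The composite SUVR, regional SUVR and antibody models name no estimator, so they show under-specification and not a demonstrated bias. The figures above would not transfer to PET either: there are two post-baseline scans (Weeks 52 and 78), and the regional SUVR model omits APOE4. The chi-square tests for responders and visual read, and the ANCOVA for antibody AUC, are unaffected.

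**Conclusion.** Wrong as written, low severity, and confined to the mixed models for the five clinical scales and their per-protocol and APOE4 subgroup fits. If SAP 5.10 is followed literally at N = 45, standard errors are about 5-6% too small. Two-sided type I error is then about 6.4% with a t reference (about 7.2% with a normal one), and the one-sided 95% intervals for treatment differences cover about 94.0%. These closed-form figures assume complete data and five mean parameters per visit; simulation of the SAP model, including 20% dropout, agrees. In the smaller planned fits the t-reference error is about 7.0-7.6% for APOE4 strata of 25 to 20 and 6.8-7.2% for a per-protocol set of 36 to 30, subject to those assumed sizes.

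The exploratory, screening-only status limits what follows from this but does not remove it, because the intervals are there to convey precision and would overstate it.

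**What to change.** In SAP 5.10, replace the estimation sentence for the clinical scales with one to this effect: *Least-squares means and treatment differences will be estimated by REML, with Kenward-Roger standard errors and degrees of freedom, and reported with 95% confidence intervals.* Satterthwaite degrees of freedom with REML would also be acceptable. This also supplies the missing noun.

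State in 5.11 that the same applies to the APOE4 subgroup fits of these models. For consistency, add the statement to the two SUVR paragraphs of 5.10 and to the antibody model in 5.9. Those places name no estimator now, so this is new text and not a replacement.

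The cost is a few sentences in the SAP and the matching estimation options in the analysis code. Design, data collection and sample size do not change. Intervals widen slightly: with the same t reference, by a factor of 1/0.943 = 1.06 at N = 45 and 1/0.894 = 1.12 in a stratum of 20.

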2.5 Exploratory Endpoints

- The change of standard uptake value ratio (SUVR) by region by the end of study.
- AUC of anti-Aβ antibody levels by the end of study.

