5.9 Analysis of Immunogenicity Variable

Anti-A β antibodies will be summarized by presenting summary statistics of raw data and change from baseline values (n, mean, standard deviation, median, range) at each scheduled visit in mITT Population and PP Population.

The Kruskal-Wallis test or analysis of variance (ANOVA) for continuous variables for baseline information will be performed for comparing the un-adjusted change among Arm 1, Arm 2 and Arm 3.

A repeated-measures mixed-effects model with treatment (Arm 1+ Arm 2 vs. Arm 3, Arm 1 vs. Arm 3 and, Arm 2 vs. Arm 3), study visit, time-by-treatment, APOE4 status, and baseline as a

covariate will be used to analyze change from baseline of anti-A β antibodies. The unstructured covariance will be used in the modelling of the within-patient errors in the analysis. For APOE4 status subgroup analysis of MMRM, APOE4 factor will not be considered in the model. AUC of Anti-A β antibodies will be used an analysis of covariance (ANCOVA) model with treatment and baseline of Anti-A β antibodies as covariate. Antibody responders will be defined as the subjects with serum antibody titer > response threshold at any visit after baseline. The number and percentage of patients will be tabulated for each treatment group in mITT Population and PP Population at each post treatment scheduled visit. Treatment differences in the proportion antibody responders will be analyzed with the Chisq test. The one-sided 95% confidence interval (CI, right side) from all visits (V1 to V13) for subjects in Arm 3 (placebo group) will be calculated as the threshold of response.

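### APOE4 status is left out of the regional SUVR model and the antibody AUC model, without a stated reason, although every companion model adjusts for it

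*SAP*

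**What the plan says.** The covariate lists are in two SAP sections.

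- **SAP 5.9, change in antibody level.** The mixed model lists "study visit, time-by-treatment, APOE4 status, and baseline as a" covariate, so APOE4 is in.
- **SAP 5.9, antibody AUC.** The model is an "analysis of covariance (ANCOVA) model with treatment and baseline of Anti-A β antibodies as covariate", so APOE4 is out.
- **SAP 5.10, the five clinical scales.** The mixed model includes APOE4 status.
- **SAP 5.10, composite SUVR.** The paragraph opens "For change from baseline of mean SUVR, A repeated- measures mixed-effects model with treatment" and includes APOE4 status.
- **SAP 5.10, regional SUVR.** The paragraph opens "For change from baseline of mean SUVR by region" and its list is "study visit, time-by-treatment, and baseline as a covariate will be used to analyze change from baseline", so APOE4 is out. The treatment contrasts and the unstructured covariance match those of the composite model.

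SAP 2.5 makes both affected outcomes exploratory: "The change of standard uptake value ratio (SUVR) by region by the end of study" and the AUC of antibody levels. SAP 5.9 gives one rule for dropping APOE4, and it applies only to the mixed model within APOE4 subgroups. SAP section 6 and the amendment history do not explain the difference; the history records removal of centre from the 5.9 model and does not mention APOE4. Protocol 9.4.3 and 9.4.4 name mixed models but list no covariates.

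**The concern.** The two affected analyses are companions to adjusted ones. Under SAP 4.3.1 the composite SUVR is a weighted average over regions, and under SAP 4.3.3 the regional analysis uses the same example regions and the same whole-cerebellum reference. A reader will look to the regions to explain the composite. The AUC likewise summarises the titres that the antibody mixed model analyses. If one of each pair is adjusted and the other is not, part of any difference between them may come from the model.

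The plan itself treats APOE4 as relevant. It is genotyped at Visit 1 (Protocol 8.1.3), used in the other models, and used for subgroup analyses of all immunogenicity and efficacy data (SAP 5.11). Protocol 3.4 describes 1:1:1 allocation and mentions no stratification by APOE4. With about 15 subjects per arm, a chance imbalance in carriers is likely enough to matter for interpretation. Leaving the covariate set unexplained also leaves room to choose it after the results are known.

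**Working it through.** The plan states no figure that depends on APOE4 adjustment, so there is none to reproduce. The main check is a term-by-term comparison. The arithmetic after it only gauges size.

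**Step 1: covariates side by side**

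| Outcome | SAP section | Status | Treatment | Visit and time-by-treatment | Baseline | APOE4 |
|---|---|---|---|---|---|---|
| Antibody change | 5.9 | primary | yes | yes | yes | yes |
| Antibody AUC | 5.9 | exploratory | yes | not applicable | yes | **no** |
| Five clinical scales | 5.10 | secondary | yes | yes | yes | yes |
| Composite SUVR | 5.10 | secondary | yes | yes | yes | yes |
| Regional SUVR | 5.10 | exploratory | yes | yes | yes | **no** |

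APOE4 is in every overall mixed model but the regional one, and it is missing from the only ANCOVA.

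**Step 2: chance carrier imbalance**

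Inputs from the documents: 15 subjects per arm, and the contrasts of each active arm with placebo (15 v 15) and both active arms with placebo (30 v 15). Assumed: carrier prevalence p of 40–70%.

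P(imbalance of 20 points or more) = the sum of Bin(i; n1, p) × Bin(j; n2, p) over all i, j with |i/n1 − j/n2| ≥ 0.20.

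| p | 15 v 15 | 30 v 15 |
|---|---|---|
| 0.40 | 0.351 | 0.238 |
| 0.50 | 0.362 | 0.248 |
| 0.60 | 0.351 | 0.238 |
| 0.70 | 0.318 | 0.206 |

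That is about 35% for 15 v 15 (32% at 70% carriers) and 21–25% for 30 v 15.

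**Step 3: what an imbalance does to the estimate**

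Shift in the unadjusted difference = imbalance × APOE4 effect. Assumed: an APOE4 effect of 0.25–0.75 SD.

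- A 20-point imbalance gives 0.20 × 0.25 = 0.05 SD up to 0.20 × 0.75 = 0.15 SD.
- SE for 15 v 15 = √(1/15 + 1/15) = 0.365 SD. The largest shift is 0.15/0.365 = 0.41 SE.
- SE for 30 v 15 = √(1/30 + 1/15) = 0.316 SD. The largest shift is 0.15/0.316 = 0.47 SE.

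**Step 4: precision**

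With 45 subjects, three arms and one baseline covariate, residual df = 45 − 4 = 41. Adding APOE4 leaves 40. The SE ratio (adjusted/unadjusted) is about √[(1 − R²) × 41/40], where R² is the share of residual variance explained by APOE4 (assumed). The equivalent gain in subjects is 1/ratio² − 1.

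| R² | SE ratio | Change in SE | Equivalent subjects |
|---|---|---|---|
| 0 | √1.025 = 1.012 | +1.2% | a small loss |
| 0.05 | √0.97375 = 0.987 | −1.3% | 1/0.97375 − 1 = 3% more |
| 0.15 | √0.87125 = 0.933 | −6.7% | 1/0.87125 − 1 = 15% more |

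Break-even: 1 − 40/41 = 2.4%. Below that, adjustment costs slightly more than it gains. The formula is exact for neither model; it approximates a complete-data analysis at one time point.

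**The case against.** The best defence is that nothing here is invalid. Omitting a baseline covariate does not bias a randomised comparison, both models keep the baseline value, and a shorter covariate list is a legitimate choice at 15 per arm. Only exploratory outputs are touched, SAP 5.10 reserves the p-values for screening, and SAP 5.13 already admits limited power for SUVR. SAP 5.11 will also show these outcomes by carrier subgroup. All of this stands, and it keeps the point minor. It does not explain the difference, though: SAP 5.13 calls the mean SUVR and the cognitive and functional analyses exploratory too, yet those models adjust. Subgroup tables are not covariate adjustment.

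A reader might infer more than the documents support, in three ways.

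- **That regional effects cannot agree with the composite because of this omission.** Each regional model has its own regional baseline and its own covariance, so the estimates need not add up even with identical covariate lists. AUC is a different summary from titre change and carries the last value forward when titres are missing (SAP 4.2). The adjustment set is only one possible source of a difference.
- **That the unadjusted results are biased.** A chance imbalance may move a particular estimate, but it does not make the comparison biased.
- **That adjustment is bound to help.** The documents do not say how much variance APOE4 explains in either outcome, and nothing in them links it to antibody response. Below about 2.4%, the standard error rises.

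**Conclusion.** The inconsistency is real and unexplained. It is a minor point of consistency and possible precision, confined to two exploratory analyses; no primary or secondary model, sample size or alpha level changes. The comparison of covariate lists rests on the text alone. The sizes in the working rest on assumed prevalence, effect and R², and the precision gain is modest even at the top of the assumed range. The case for alignment is that the factor is already collected and already used in the companion models, and that the worst case in this calculation is a standard error about 1.2% larger.

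**What to change.** Before unblinding, make two edits to the SAP.

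- **SAP 5.10, regional SUVR:** add APOE4 status to the fixed effects of the overall mixed model, coded as in the composite model.
- **SAP 5.9, antibody AUC:** add APOE4 status to the overall ANCOVA, alongside treatment and baseline antibody level.

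Leave APOE4 out of the APOE4 subgroup runs of both models, extending to the ANCOVA the rule that SAP 5.9 already sets for the mixed model. If the omission was deliberate, the SAP should instead give the reason.

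The cost is one phrase in each of two sentences and one degree of freedom in each model. No new data are needed.

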## 9.4 Statistical Methods

Continuous data will be summarized by treatment group using the number of observations available (n), mean, standard deviation (SD), median, interquartile range (IQR), minimum, and maximum.

Categorical data will be summarized by treatment group using count and percentage. Missing data will not be categorized in the summaries.

In general, descriptive statistics of quantitative efficacy and safety parameters (results and changes from baseline) by scheduled visit will be provided on observed cases, i.e. the inclusion of only subjects with non-missing assessments at a specific visit.

All statistical tests will be two-sided at the alpha level of 0.05.

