4 ANALYSIS VARIABLES

4.1 Demographic and Baseline Characteristics

The baseline value is defined as the last available value before the first injection of study drug. The following demographic and baseline disease characteristics will be summarized by treatment, by study center and overall for the randomized and treated population.

Demographic characteristics are defined as follows:

- Age (in years) to be derived as: (date of informed consent - date of birth)/365.25
- Gender (male/female)
- Body weight (kg)
- Body Mass Index (BMI, kg/m²): weight in kg/(height in meters)²
- Race

Disease characteristics including:

- Disease duration (years): (date of informed consent– date of diagnosis)/365.25
- APOE genotype
- Baseline scores of ADAS-Cog total score, MMSE total score, ADCS-ADL total score, CDR/CDR-SB total score, NPI total score

Inflammatory markers including:

- CRP
- ESR
- TNF- α
- IL-6
- IL-8

Physical examination, medical history and concomitant disease, previous and concomitant medication, and HIS score will be described at baseline.

The baseline safety data of clinical chemistry and hematology, inflammatory markers and number of microhemorrhages in the brain will also be summarized.

4.2 **Immunogenicity Variables**

The level of anti-A β antibodies is one of the primary endpoints and is assessed at baseline (V1) and every following visit (V2 to V13). The one-sided 95% confidence interval (CI, right side) from all visits (V1 to V13) for subjects in Arm 3 (placebo group) will be calculated as the threshold of response. Antibody responders will be defined as the subjects with serum antibody titer > response threshold at any visit after baseline.

Response rate, treatment difference and its 90% CI will be calculated.

The AUC of anti-A β antibodies will be served as exploratory endpoint. AUC will be calculated by the sum of individual trapezoid area under the curve of level of A β antibodies. In case of missing titer values, last observation carry forward will be used for AUC calculation.

4.3 **Efficacy Variables**

Efficacy variables are evaluated as secondary endpoints in this study.

The change from baseline in cognitive, functional, and global assessments through the end of the study

- Cognition: ADAS-Cog
 - The ADAS-cog 13 contains 13 items, with a total scoring range of 0 – 85 and higher scores indicating greater dysfunction.
- Cognition: MMSE

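### SAP 5.10 reports efficacy differences with one side of a 95% confidence interval, mostly without naming the side, although tests are two-sided and the scales run in opposite directions

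*SAP*

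**What the plan says.** SAP 5.10 fits a repeated-measures mixed model to change from baseline in the five scales, composite SUVR and regional SUVR. The contrasts are pooled active, Arm 1 and Arm 2, each against placebo. For the precision of these contrasts it says that "one side of 95% confidence intervals are provided to help gauge the precision of the estimates for treatment difference". The side is not named. For the proportion of subjects who are PET positive on visual read, the side is named: "The one-sided 95% confidence interval (CI, right side) between (Arm 1 + Arm 2 vs. Arm 3" and the two single-arm contrasts.

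Three other statements bear on this:

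- **Tests.** SAP 5.1 has "All statistical tests will be two-sided at the alpha level of 0.05, unless otherwise specified", and Protocol 9.4 has "All statistical tests will be two-sided at the alpha level of 0.05".
- **Least squares means.** In the rating-scale paragraph, SAP 5.10 has "The least square means using maximum likelihood estimate and its 95% will be provided". The noun after the percentage is missing, and the sentence concerns means, not differences. The two SUVR paragraphs have no such sentence.
- **Scale direction (SAP 4.3).** For ADAS-Cog, "higher scores indicating greater dysfunction", and CDR-SB runs the same way. For ADCS-ADL, "score is range of 0-78 and lower scores indicating greater impairment", and MMSE runs the same way. NPI is described as if lower scores were worse.

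Neither document promises a two-sided interval for an efficacy treatment difference. For the responder-rate difference, SAP 4.2 uses a 90% interval.

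**The concern.** Three things do not fit together.

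1. The stated purpose is to show precision. Readers take precision from the width of an interval, and a one-sided interval has no width.
2. The tests and the limits use different error rates, so a table could show a limit that excludes zero beside a p-value above 0.05.
3. With scales that run in opposite directions, the meaning of one side changes from endpoint to endpoint. With the side unnamed, two programmers could produce different tables from the same plan, and the side could be chosen after results are known.

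What is at stake is how the secondary results are read. SAP 5.13 concedes that there is very little power for cognition and function, and SAP 5.10 gives the efficacy p-values only a screening role. A screening decision on these endpoints should rest on the estimate and on the range of benefit and harm that the data still allow.

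**Working it through.** The plan gives no figure for efficacy precision, so there is none to reproduce. Its only design figures concern detection of adverse events and play no part here.

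**Inputs.** Planned arm sizes are 15 per arm, so pooled active versus placebo is 30 v 15 (SAP 5.13). The test level is two-sided 0.05 (SAP 5.1). The documents give no SD for any efficacy endpoint, so distances are in SD units. Assumptions: a two-sample comparison at one time point, full enrolment, no dropout, no covariate adjustment.

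**Step 1: limit against test.** A one-sided 95% limit uses z = 1.645, as does each end of a two-sided 90% interval. A two-sided 95% interval uses z = 1.960. The one-sided limit that faces zero therefore excludes zero as soon as two-sided p falls below 0.10, while the test rejects only below 0.05.

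**Step 2: distance from estimate to limit.** SE = SD × √(1/n₁ + 1/n₂), and distance = t × SE.

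| Contrast | SE (SD units) | df | t, one-sided 95% | Distance | t, two-sided 95% | Distance |
|---|---|---|---|---|---|---|
| 30 v 15 | √(1/30 + 1/15) = 0.316 | 43 | 1.681 | 0.53 | 2.017 | 0.64 |
| 15 v 15 | √(1/15 + 1/15) = 0.365 | 28 | 1.701 | 0.62 | 2.048 | 0.75 |

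The ratio of the two distances does not depend on the SD: 1.681/2.017 = 0.83 and 1.701/2.048 = 0.83. The limit shown sits about 17% closer to the estimate than a two-sided 95% limit would.

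**Step 3: where limit and test disagree.** For 30 v 15, this happens for an observed difference between 0.53 and 0.64 SD in either direction, if the side reported is the one facing zero. With a difference of 0.60 SD, the facing one-sided limit is 0.60 − 0.53 = 0.07 SD and excludes zero. The matching two-sided 95% limit is 0.60 − 0.64 = −0.04 SD and does not. The test statistic is 0.60/0.316 = 1.90, between 1.681 and 2.017, so p is between 0.05 and 0.10.

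**Step 4: what an unnamed side allows.** Take 15 v 15 and an assumed difference of −0.30 SD. Upper limit only: −0.30 + 0.62 = +0.32 SD. Lower limit only: −0.30 − 0.62 = −0.92 SD. Two-sided 95% interval: −1.05 to +0.45 SD. All three describe the same data.

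**Step 5: direction.** Take active minus placebo and one fixed side.

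| Endpoint | Worse direction (SAP 4.3) | Upper limit only bounds | Lower limit only bounds |
|---|---|---|---|
| ADAS-Cog, CDR-SB | higher | harm | benefit |
| MMSE, ADCS-ADL | lower | benefit | harm |
| NPI, as written | lower | benefit | harm |

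The NPI row depends on a direction that looks doubtful. SAP 4.3 describes 12 domains, a 4-point frequency and a 3-point severity, and 12 × 4 × 3 = 144 is the stated maximum. That suggests a total that rises with symptom burden. If so, NPI moves to the first row.

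**Step 6: is precision lost?** No. SE = (limit − estimate)/t. From Step 4, (0.32 + 0.30)/1.701 = 0.365 SD, the SE in Step 2. A reader who has the estimate, the limit and the degrees of freedom can rebuild the two-sided interval.

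**The case against.** The strongest reply is that little depends on these limits. Efficacy is secondary, SAP 5.13 treats it as exploratory, there is no multiplicity adjustment, and no decision rule uses an efficacy limit. The primary objectives are safety, tolerability and immunogenicity, and safety has its own analysis in SAP 5.12. This stands, and it caps the importance of the point.

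A reader might also infer three stronger things that the documents do not support:

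- **That harm is left unbounded on some scales.** This follows only if one fixed side is used for every scale. SAP 5.10 names no side for the scales or SUVR. If the side followed each scale's direction, harm could be bounded on all of them, with benefit left open instead. In particular, no right-sided limit is planned for MMSE.
- **That precision cannot be read.** Step 6 shows that it can be recovered exactly. Two-sided p-values and by-visit summaries with n and SD are also planned. Precision is not displayed, but it is not lost.
- **That the named right side for PET shares the problem of opposite directions.** It is a single outcome, and every subject must be amyloid positive at entry, so no conflict of direction arises within it. It still shows only one limit and does not match the two-sided test.

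The planned least squares means with a 95% figure do not answer the point. That sentence is incomplete, covers the rating scales only, and concerns arm means rather than differences.

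**Conclusion.** The point holds as a reporting defect. SAP 5.10 gives one limit for each efficacy difference, does not name the side for the scales and SUVR, and pairs it with tests at a different error rate. Limit and test can disagree for p between 0.05 and 0.10, which for 30 v 15 means observed differences of about 0.53 to 0.64 SD. The limit shown lies 0.53 SD from the estimate instead of 0.64 SD; for 15 v 15 the figures are 0.62 and 0.75 SD.

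The SD-unit distances rest on planned arm sizes, no dropout and an unadjusted comparison at one visit. Dropout would lengthen them, and adjustment for baseline and APOE4 could shorten them. The mismatch between limit and test depends on none of these. The change should be made, but the point does not touch the primary endpoints.

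**What to change.** In SAP 5.10, replace both one-sided statements with two-sided 95% confidence intervals for every efficacy treatment difference: the five scales, composite SUVR, regional SUVR and the PET-positive proportion. State the subtraction order once (for example, active minus placebo) and list the favourable direction for each endpoint beside it. Complete the sentence on least squares means so that it names the interval. Check the NPI direction in SAP 4.3 against the scoring instructions, because it decides which side of the interval is harm.

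The cost is SAP wording and the matching table layouts, best settled before unblinding. No new data, visits or subjects are needed, and the models and tests do not change.
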